No. medical charts requiring detailed chart review including preparation of PowerPoint synopsis and then further Triage MD review	311	An unknown number of cases will be diagnosed as TACO and will have no evidence for ALI; these will not need to be forwarded to the Medical Review Board for adjudication. Total number of forwarded charts will be less than 311

F6. Pilot study to validate assumptions for proportions of patients with chest x-ray, pulmonary edema, and hypoxemia: A medical record review was conducted at Pittsburgh Center by research nursing staff on 66 randomly selected units of FFP transfused to 66 patients in Pittsburgh area hospitals. Twenty two patients were at a community hospital and 44 patients at a tertiary care hospital. Chest x-ray data was extracted from a radiology electronic database with radiologist's interpretation. A chest x-ray was considered present if done within 24 hours of the end of the index transfusion. Those reports indicating pulmonary edema, bilateral pulmonary congestion or bilateral infiltrates were then evaluated for hypoxemia. Hypoxemia was sought in the laboratory section of the patient's electronic medical record and was defined as: SO2/FiO2 of <315 or pO2/FiO2 of <300 within 6 hours of the end of the FFP transfusion.

At the community hospitals, 5 of the 22 (23%) had a chest x-ray within 24 hours of the transfusion; 3 of the 5 (60%) had pulmonary edema, and 2 of the 3 (66%) had hypoxemia. At the community hospitals, 2 of the 22 (9.1%) of the recipients would require an extended record review.

At the tertiary care hospitals, 24 of the 44 (55%) recipients had a chest x-ray within 24 hours of the transfusion. Twelve of the 24 (50%) had pulmonary edema and 6 of the 12 (50%) had hypoxemia. These data indicate that 6 of 44 FFP transfusion recipients at tertiary care hospitals would require extended record review.

It should be noted that of the six recipients at the tertiary care hospitals who had pulmonary edema on chest x-ray after the transfusion, four had pre-existing pulmonary edema on pre-transfusion chest x-ray.

The above pilot study supports our assumptions regarding the stepwise record review process.

F7. REDS-II Blood Centers to identify blood components from LAPS donors:

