F16. Identification of study recipients, record retrieval, medical records review, and data collection: Hospital blood bank staff will identify the disposition of study blood components. For those components that were issued for transfusion, the blood bank staff will complete a form that indicates that the component was issued for transfusion, name of the patient, the patient's medical record number, blood unit identification number, the date and time the product was issued, type of component and whether there was any adverse event reported within 24 hours after the issue of the product.

The record review coordinator will record information from those patients who had a chest x-ray within 24 hours after the blood component was issued for transfusion. Each center will need to work with their hospitals to find the best way to review radiology records. The radiologist's interpretation of each chest x-ray will be transcribed verbatim on to a data collection form

provided by the Coordinating Center and forwarded to the site investigator. The site investigator will review the radiology reports and determine which patients' charts will require further detailed review. The site investigator review and decision will be documented on to a data collection form. The record review coordinator will request the medical charts from the medical records department. At some hospitals, electronic records may be available and the coordinator may access the electronic records after having been approved to do so. Digital images of chest x-rays will be obtained for cases that need the triage physician and Expert panel reviews when available.

F17. Record review coordinator qualification and training: Qualifications of personnel engaged in record review can include medical technologists; nurses with critical care unit or operating room experience; respiratory care professionals; and other suitable individuals. The designated individuals at each Center will be provided with reading material and will undergo training at [name] program which will involve review of actual cases of TRALI, Acute lung injury (ALI), TACO, and transfusion recipients without these complications. The nurses working with [name] prospective study on TRALI who are very familiar with record reviews will provide training. The training will also include writing up case summaries for the Medical Review Board.

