A list of the components that were supplied to each participating hospital will then be printed by the blood center and provided to each corresponding transfusion service medical director or designated individual to identify corresponding recipients and to have the radiology and the medical records be abstracted by the record review coordinator(s). All information will be tracked and compiled into the tracking and data management systems either directly by research staff at the blood center/blood bank or by Westat, if forms are mailed to the coordinating center for data entry.

The coordinating center will be responsible for formation of the medical review board. The medical review board will assess all completed data forms in a blinded manner to determine the presence or absence of TRALI as described above. The coordinating center will compile the results of these reviews into the data management system to allow for formation of a database that will be used for analyses. The proposed diagnostic criteria for TRALI are detailed in the next section.

F25. Proposed Diagnostic criteria for TRALI: Using the Canadian Consensus Conference criteria, the medical review board will be responsible for reviewing the completed recipient forms and determining the presence or absence of TRALI (Kleinman et al).

- 1. New hypoxemia must be present and hypoxemia is defined as pO2/FiO2 ratio of <300 within 6 hours of completion of transfusion or venous oxygen saturation (SpO2) of less than 90% on room air; or other clinical evidence of hypoxemia (e.g., cyanosis). Based on the recent report from Rice TW et al., additional criteria to determine hypoxemia representative of ARDS will be included as follows: ratio of SpO2/FiO2 <315; where FiO2 will be calculated for patients receiving oxygen by cannula or mask as follows: 1 liter = 0.21; 2 liters = 0.23; 3 liters = 0.25; 4 liters = 0.3; 5 liters = 0.35; 6 and 7 liters = 0.45, and 8,9, and 10 liters = 0.49 (Rice TW 2007).
- 2. Bilateral infiltrates on frontal chest radiograph (obtained within 24 hours of Completion of transfusion) must be present. There must be absence of left atrial hypertension (i.e., circulatory overload). However, if ALI is diagnosed by the expert panel in the presence of left atrial hypertension, the case may be classified as TRALI/TACO (overlap case).

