G.1. Limitations of retrospective medical record review: One of the limitations of a retrospective medical record review study is that some clinical findings may not be recorded in a patient's chart. However, it is highly unlikely that major clinical findings such as severe respiratory distress would not be recorded. Conversely, milder signs and symptoms may not be recorded and it is therefore possible that milder cases of TRALI (e.g., those in which hypoxemia is not severe) as well as milder cases of pulmonary dysfunction that fall short of the diagnosis of TRALI may be missed. However, TRALI experts are unsure if mild forms of TRALI exist. Since certain clinical data are almost always recorded including arterial blood gas analysis results, chest x-ray interpretations, electrocardiogram results, brain natriuretic peptide (BNP) measurements, echocardiogram interpretation, white blood cell counts, and vital signs including temperature, the retrospective study design proposed in this research should allow for comprehensive detection of clinically-significant forms of TRALI.

A large number of blood recipients must be studied to confidently identify a difference in TRALI risk from an antibody positive vs. antibody negative component. To accomplish this practically, a stepwise method for recipient record review is proposed. First, a patient must have had a chest x ray within 24 hours of the time the blood was issued. Second, the radiology report must indicate the presence of new or worsening bilateral lung infiltrates/pulmonary edema for the patient's record to be reviewed further. Third, hypoxemia must be documented. Fourth, a critical care specialist will review the cases at this point primarily to exclude or triage cases of TACO

prior to forwarding the case to the medical board for review. Since a retrospective data collection study is by design inefficient compared to a prospective study, this stepwise approach described reduces the labor needed for medical record review and yet allows follow up of a large number of recipients.

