Appendix F: Screening Form

LEUKOCYTE ANTIBODIES PREVALENCE STUDY – PHASE II SCREENING FORM

STUDY ID LAREL

SECTION A: HOSPITAL Tx SERVICE FORM [completed by hospital Tx service staff]

DATE:				COMPL	COMPLETED BY:						
BUI#:	ТҮРЕ С		OF COM	COMP:			Tx UN	IT #:			
DATE OF ISSUE:				TIME OF ISSUE: (Military Time)							
HOSPITA	L:										
	SERVICE ISSUED TO (Record if information is available. See Note 1): (Med, Surg, Ob/Gyn, Heme/Onc, OutPt, OR, ICU, Recovery, etc.)										
PATIENT (Last, First, N			MED REC #:								
BIRTHDA	TE:				GEN	IDER:	MAI	LE 🗌	FE	MALE	
PATIENT (Check one)	AB0/RH:	[0+	0-	A+ □	A-		B+	B-	AB+	AB-
Tx REACT	TION:	`	YES 🗌	NO 🗌							
TYPE OF ((Describe):	REACTIO	N									

SECTION B: HOSPITAL FORM [completed by Med Tech/ Coordinator]

DATE:			ABSTRACTED BY:						
SOURCE OF INFORMATION:									
ELECTRONIC RADIOLOGY REPORTS DATABASE									
ELECTRONIC MEDICA	L RECO	ORDS INCLUDING	G RADIOLOGY REPOR	rs 🗌					
PAPER MEDICAL REC	ORDS								
OTHER (SPECIFY)									
			DATE	TIME (Military Time. See Note 2.)					
PRE Tx CHEST X-RAY (If yes, record date & time of up to 3 X-rays)		YES 🗌 NO [
POST Tx CHEST X-F (If yes, record date & of up to 3 X-rays)		YES 🗌 NO [

DISCHARGE DIAGNOSIS (If electronically available): List up to 10 diagnosis Assign ICD-codes	DESCRIPTIVE DIAGNOSIS	ICD CODE
1.		
2.		
3.		
4.		
5.		
6.		
7.		
8.		
9.		
10.		

If NO post transfusion chest X-ray within 24 hrs of issue of blood product then end now

PRE TRANSFUSION CHEST X-RAY REPORT: (Please write complete report. If more than one, include all reports.)

POST TRANSFUSION CHEST X-RAY REPORT: (Please write complete report. If more than one, include all reports)

SECTION C: PI REVIEW FORM [completed by PI or designee nurse/MD]

DATE OF REVIEW:		REVIEWED BY:						
EXTENDED CHART REVIEW:		YES NO						
BILATERAL LUNG INFILTRATES	NARY EDEMA	ARDS						
YES 🗌 NO 🗌	YES 🗌	NO 🗌	YES 🗌	NO 🗌				
WORSENING PULMONARY EDEMA	1	NEW PULMONARY EDEMA						
YES 🗌 NO 🗌		YES D NO D						
PI RECCOMMENDATION: Proceed	with cha	art review?	YES 🗌	NO 🗌				
COMMENTS:								

If NO extended chart review required then end now ENTER FORM DATA IN SMS. DO NOT ENTER DATA SHADED IN YELLOW.

NOTES:

- 1. Service to which the product was issued from the blood bank may not always be available. For those products issued to the operating room (OR) or the recovery room, note that the issue time may differ significantly from the transfusion time since these locations may have temporary storage facility.

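### The first x-ray screen closes 24 hours after issue, before the endpoint's window of 24 hours after completion of transfusion, so some recipients who could meet the TRALI criteria are never reviewed

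*Protocol*

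**What the plan says.** The protocol runs one x-ray requirement on two clocks.

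**Counted from issue.**
- Appendix F, Screening Form, stop rule: "If NO post transfusion chest X-ray within 24 hrs of issue of blood product then end now".
- F16: the coordinator records information from patients "who had a chest x-ray within 24 hours after the blood component was issued for transfusion".
- G1, first step of the stepwise review: "a patient must have had a chest x ray within 24 hours of the time the blood was issued".
- F3: the 106-component pilot that gives the 40% planning figure also counted 24 h from issue.

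**Counted from transfusion, or its end.**
- F25, item 2: "Bilateral infiltrates on frontal chest radiograph (obtained within 24 hours of Completion of transfusion) must be present".
- F6, pilot of 66 plasma units: "A chest x-ray was considered present if done within 24 hours of the end of the index transfusion".
- C1, the review procedure in F3, Section I and Note 2 of the Screening Form all refer to the transfusion, not to issue.

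Note 1 of the Screening Form recognises that the clocks diverge. For units sent to the operating or recovery room, coordinators should "note that the issue time may differ significantly from the transfusion time since these locations may have temporary storage facility". The form has fields for date and time of issue, but none for the start or end of transfusion.

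**The concern.** A screening step should be at least as wide as the endpoint that it feeds. Here it is narrower, and a recipient stopped at this step does not go on to the site investigator, the triage physician or the expert panel. Such a recipient stays in the denominator of the Section L comparison without being counted as TRALI.

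Three things are at stake:
- Section L plans absolute incidence per unit and per recipient. Missed cases bias those estimates downward even if both arms lose them equally.
- Appendix H recalculates the sample size from the observed, still blinded, TRALI incidence.
- With both anchors in the text, the five centers may apply different windows.

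G1 admits that films taken more than 24 h after the transfusion will be missed. It does not say that films inside that period can be missed too.

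**Working it through.** **1. The plan's own figures.** F23 and Appendix D give 2.32% (case recipients) and 0.79% (control recipients). With 1,295 per group, 1,295 × 0.0232 = 30.0 and 1,295 × 0.0079 = 10.2, which matches the 30 + 10 = 40 cases in F23 and F26. Appendix D states 90% power for 1,175 per group with a one-sided 0.05 exact conditional test. Power was computed as the sum, over all pairs (x1, x2), of Bin(x1; 1,175, 0.0232) × Bin(x2; 1,175, 0.0079) wherever the one-sided Fisher p-value is at most 0.05. The result is 90.0%, so the stated power reproduces.

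**2. The gap between the windows.** Let I be the time of issue, E the time of completion, and L = E − I, which is greater than zero.
- The screen closes at I + 24 h.
- The F25 window closes at E + 24 h = I + 24 h + L.
- A recipient with no film up to I + 24 h, and a film between I + 24 h and I + 24 h + L, is stopped although the film is acceptable under F25. The gap is exactly L hours.

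**3. Recipients affected.** G1 gives x-ray rates of 42% for 24 h and 52% for 48 h. Three assumptions are needed: these rates run from issue (G1 does not name the anchor), films accrue linearly between the two times, and L takes the values shown (no lag is documented).
- Slope = (52 − 42) / 24 = 0.417 points per hour.
- Points lost = 0.417 × L.
- Recipients = 2,590 × points / 100.
- Share of those with an acceptable film = points / (42 + points).

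| Assumed L | Points | Recipients of 2,590 | Share of those with an acceptable film |
|---|---|---|---|
| 1 h | 0.42 | 11 | 1.0% |
| 2 h | 0.83 | 22 | 1.9% |
| 4 h | 1.67 | 43 | 3.8% |
| 6 h | 2.50 | 65 | 5.6% |
| 12 h | 5.00 | 130 | 10.6% |

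**4. TRALI cases affected.** The recipients in step 3 have a film of any kind; they are not TRALI cases. If cases were lost in the same proportion, a lag of 2 to 6 h gives 40 × 0.019 = 0.8 to 40 × 0.056 = 2.2, or roughly 1 to 2 cases over both arms.

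**5. Power.** Both rates were multiplied by (1 − loss) and the calculation in step 1 repeated at 1,175 per group.

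| Cases lost in each arm | Exact power |
|---|---|
| 0% | 90.0% |
| 2% | 89.4% |
| 5% | 88.5% |
| 10% | 86.7% |

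A loss of 2% to 5% therefore costs 0.6 to 1.5 points.

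**The case against.** **The window was chosen and piloted.** G1 compares 12, 24 and 48 h and accepts the loss of later films, a 10-point difference beside which a shift of a few hours is small. Issue time is what the blood bank supplies for every unit. The 106-component pilot in F3 used the issue window, so the 40% workload figure does belong to the form's rule. All of this stands. It justifies the length of 24 h, but it does not explain why the screen and the endpoint start from different times.

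**True cases are likely to be filmed early.** F25 requires hypoxemia within 6 h of completion, and a patient is lost only if no film at all was taken in the 24 h after issue. This also stands, and it makes the proportional figure of 1 to 2 cases more likely too high than too low.

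**Films taken before transfusion.** A reader might infer that a film taken between issue and completion ends up counted as post-transfusion in the diagnosis. The documents do not support that. The stop rule asks for a post-transfusion film, the form has separate pre and post rows with date and time, and Note 2 ties them to the study unit's transfusion. The Extended Form records a date and time of transfusion, and the panel applies F25. What remains is an ambiguity at screening, which later review can catch. Nor can G1's 12-hour rate be turned into a share of misclassified films, since a patient filmed early may be filmed again after transfusion.

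**Who is affected.** A reader might infer that the loss falls mainly on surgical plasma recipients. Note 1 names operating and recovery rooms but gives no frequency and does not single out plasma.

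**Conclusion.** The conflict is real and follows from the text alone: the stop rule can end review of recipients who would meet the x-ray criterion in F25, and G1 does not disclose this. Its size is uncertain and probably small. For an assumed lag of 2 to 6 h it is about 22 to 65 of 2,590 recipients, roughly 1 to 2 of the 40 projected cases if lost in proportion, and about 0.6 to 1.5 points of power if 2% to 5% of cases are lost. These figures rest on the assumed lag, on G1's rates running from issue, and on linear accrual.

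A reader might also infer bias between the arms. Nothing in the protocol shows it: reviewers are blinded to antibody status and the same rule applies to both groups. The consequence is slight under-ascertainment of incidence. It merits correction because the rule contradicts the endpoint definition and the correction is cheap.

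**What to change.** 1. Make the screening window at least as wide as the endpoint window. End review only if there is no chest x-ray within 24 h after the end of transfusion. Where that time is not available at screening, use a wider window from issue. For example, 30 h covers lags up to 6 h; the value should be set from the observed lag between issue and completion.
2. Add the transfusion time to the Screening Form, so that films are classed as pre or post by transfusion and not by issue.
3. Apply the F25 window at adjudication, so that the wider screen does not loosen the endpoint.
4. Use one anchor in F16, G1, Section I and Appendix F.

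The cost is one added time field, the edits to those sections, and a few dozen more x-ray reports: up to about 65 over five centers at the 6 h lag, or 65 / 5 = 13 per center.

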F4. Review to detect presence or absence of hypoxemia indicative of ARDS: In order to further eliminate the unnecessary detailed record review, a focused review of the transfusion episode will be performed to detect hypoxemia occurring within six hours of completion of transfusion. Medical records will be reviewed for the respiratory status within six hours after the completion of the study unit transfusion to detect the following: Oxygen saturation (SpO2) less than 90% by pulse oxymetry without or with oxygen therapy; ratio of SpO2/FiO2 <315; and ratio of PaO2/FiO2 <300 on arterial blood gas analysis. FiO2 will be calculated for patients receiving oxygen by cannula or mask as follows: 1 liter = 0.21; 2 liters = 0.23; 3 liters = 0.25; 4 liters = 0.35; 6 and 7 liters = 0.45, and 8, 9, and 10 liters = 0.49 (Rice TW 2007).

If hypoxemia is documented, a detailed medical record review will be performed by the record review coordinator. The full extended data form will be completed. A Power Point summary of the major events and timeline will be prepared. The completed extended data forms and summaries will be sent to the Triage MD for further review.

Precise incidence rates for hypoxemia as defined in this manner in hospitalized patients are not available. Most of the data on incidence of acute respiratory failure (ARF) are reported in patients who are treated in the intensive care unit (ICU). For example, Flaatten et al have reported an incidence of ARF of 63% among 832 patients treated in the ICU. In 13,346 ICU admissions, 1,231 (9.2%) patients were found to have acute respiratory failure by Luhr et al. Pettila et al have described an incidence of ARF of 32.5% in 520 ICU patients while Vincent et al found that 32% of the 458 ICU patients had ARF at admission to the ICU and 35% of the 991 ICU patients developed ARF during their stay in ICU. Roupie et al report that 43% of the ICU patients required mechanical ventilation. A combined rate of 16% for ARDS and ALI in 1977 ICU admissions has been observed by Bersten et al. These data show a wide range for ARF in ICU patients. In order to be more conservative in our estimates for the number of charts requiring detailed review, we have estimated that 60% of the study patients would have hypoxemia/acute respiratory failure and would therefore require detailed chart review along with a review by a triage critical care physician (see below).

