
Estimate FiO2 as follows, if patient is receiving oxygen by nasal cannula or mask.

Room air: 0.21	1 Liter of O2: 0.23	2 Liters of O2: 0.25	3 Liters of O2: 0.27
4 Liters of O2: 0.30	5 Liters of O2: 0.35	6, 7 Liters of O2: 0.40	8, 9, 10 Liters of O2: 0.49

If receiving oxygen therapy with mechanical ventilation, use percent oxygen recorded on the patient's respiratory care data. Review ventilator data to find FiO2 value (eg. 405 oxygen administration equals a FiO2 of 0.4).

RESPIRATORY STATUS	YES	NO	NR
Oxygen saturation (SpO2) less than 90% by pulse oxymetry without oxygen therapy?			
Oxygen saturation (SpO2) less than 90% by pulse oxymetry while receiving oxygen therapy			
Ratio of SpO2/FiO2 <315 (See Note 1)			
Ratio of PaO2/FiO2 <300 (PaO2 = oxygen saturation on arterial blood gas analysis) (See Note 2)			

If answer to **ANY** of the above respiratory status items is **YES** then further chart review is required. If answer to **ALL** of the above respiratory status items is **NO** then stop now and send copy of form to Westat.

NO.	ITEM	YES	NO	NR	START DATE (If applicable)	RESOLVE DATE (If applicable)	NOTES
1	Acute CNS Injury (within 7 days before Tx)				applicable)	applicable)	Note 3
2	Acute renal failure (within 7 days before Tx)						Note 4
3	Aspiration						Note 5
4	Bone marrow stem cell transplant in past 12 months						
5	Burn as an admitting diagnosis (if within 48 hrs before reaction)						
6	Cancer or recent (within 1 month) chemotherapy						
7	Cardiac bypass during current admission (within 48 hrs before reaction)						
8	Cardiac ischemia during current admission (within 7 days before Tx)						
9	Hx of chronic alcohol abuse						Note 6
10	Hx of chronic renal failure						Note 7
11	Congestive heart failure during current admission (within 7 days before Tx)						Note 8
12	Hx of coronary artery disease						
13	Hx of diabetes mellitus						Note 9
14	DIC during current admission (within 7 days before Tx)						Note 10
15	Drug overdose as admitting diagnosis (within 48 hrs before reaction)						
16	Exposure to high altitude as admitting diagnosis (within 48 hrs before reaction)						
17	Heat stroke as admitting diagnosis (within 48 hrs before reaction)						
18	Hemorrhagic shock during current admission (within 48 hrs before reaction)						
19	High INR (>3.0) during current admission (within 7 days before Tx)						
20	Hx of immunosuppression						
21	Just underwent surgery (within 48 hours)						

SECTION F: PATIENT HISTORY & CLINICAL FINDINGS

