1	Post-transfusion fever ((temp above 100.4F or 38C) within 6 hrs				
2	Post-transfusion chills within 6 hrs without fever				
3	Acute hemolytic transfusion reactions within 24 hrs				
4	Delayed hemolytic transfusion reaction within 7 days				
5	Minor allergic (skin rash) within 6 hrs				
6	Severe allergic (anaphylactic) within 6 hrs				
7	Post-transfusion bacterial sepsis within 24 hrs				
8	Cardiac/fluid overload or congestive heart failure within 6 hrs				
9	Post-transfusion shortness of breath/dyspnea within 6 hrs				
10	Post-transfusion hypotension (systolic BP <90 mmHg) within 6 hrs				
11	Post-transfusion hypertension (systolic BP >140 mmHg) within 6 hrs				
12	Post-transfusion shock				
13	Post-transfusion O2 sat <90% on pulse oxymetry (SpO2) with or without O2 administration within 6 hrs				
14	Post transfusion ratio of SpO2/FiO2 <315 within 6 hrs				
15	Post-transfusion arterial blood gases within 6 hours after completion of transfusion showing pO2/FiO2 <300 mm Hg				
16	Post-transfusion lung auscultation reveals rales(crackles) within 24 hrs				
17	Post-transfusion lung auscultation reveals rhonchi within 24 hrs				
18	Post-transfusion elevated jugular venous pressure within 6 hrs				
19	Post-transfusion hepatojugular reflux detected within 6 hrs				

NO.	ITEM	YES	NO	NR	NOTES
20	Post-transfusion cyanosis within 6 hrs				
21	Post-transfusion central venous catheter measured elevated central venous pressure (>8 mm Hg) within 6 hrs				
22	Post-transfusion central catheter measured elevated pulmonary artery wedge pressure (>20 mm Hg) within 6 hrs				
23	Post-transfusion peripheral pitting edema detected within 24 hrs				
24	Post-transfusion, was there a loss of 4.5 kg weight in 72 hours after diuretic treatment				Note 22
25	Clinically suspect TRALI within 6 hrs				
26	Post-transfusion diagnosis of ARDS within 24 hrs				
27	Post-transfusion, patient required ICU admission within 24 hrs				Note 23
28	Post-transfusion, required vasopressures to support blood pressure within 24 hrs (e.g., dopamine, norepinephrine, epinephrine)				
29	Rapid resolution of lung infiltrates on chest X-ray after diuresis or dialysis within 6 hrs				

SECTION K: OTHER BLOOD COMPONENTS AND FLUID ADMINISTRATION

NO.	COMPONENT/FLUID	PRE-Tx AMOUNT (24 hour before Tx of the study unit started) Record if applicable	POST-Tx AMOUNT (24 hours after the Tx of the study unit finished) Record if applicable
1	RED BLOOD CELLS (No. of Units)		
2	PLATELETS, WHOLE BLOOD (No. of units)		

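### The hypoxemia screen before adjudication omits one limb of the protocol's own TRALI definition and gives no rule for unrecorded oxygenation

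*Protocol*

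**What the plan says.** - **Endpoint (F25, item 1).** New hypoxemia is required. It may be shown by PaO2/FiO2 below 300 within six hours, by SpO2 below 90% on room air, "or other clinical evidence of hypoxemia (e.g., cyanosis"), or by SpO2/FiO2 below 315.
- **Screen in the body (F4).** The criteria are SpO2 below 90% with or without oxygen and the two ratios. Then: "If hypoxemia is documented, a detailed medical record review will be performed by the record review coordinator". G1 likewise makes documented hypoxemia the third step of the review.
- **Screen on the form (Appendix G, Section E).** Four items are answered YES, NO or NR: SpO2 below 90% without oxygen; "Oxygen saturation (SpO2) less than 90% by pulse oxymetry while receiving oxygen therapy"; SpO2/FiO2 below 315; and "Ratio of PaO2/FiO2 <300". With any YES, "then further chart review is required". If all are NO, "then stop now and send copy of form to Westat".
- **Where cyanosis is recorded.** Section J, item 20: "Post-transfusion cyanosis within 6 hrs". Section J comes after the Section E stop.
- **No bypass.** F2 puts cases already reported to the blood bank through the same process.

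**The concern.** A screen that controls entry to adjudication should be at least as wide as the endpoint being adjudicated. Here one of F25's own routes to hypoxemia cannot by itself bring a recipient to the panel. In addition, the form offers a third answer, NR, that its decision rule does not use.

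The two gaps meet in one kind of chart: bilateral infiltrates, no oxygenation value recorded in the six-hour window, and cyanosis noted. F25 item 1 is met. Section E gives no instruction, and F4's list of measured criteria is not satisfied. A coordinator following F4 and G1 would probably stop, while one following the form literally would not.

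What is at stake is the completeness of case finding, the incidence estimates in section L, and the consistency of the screen across five centers and the 29 candidate hospitals, which have a mix of paper and electronic records.

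**Working it through.** **1. Routes to hypoxemia, side by side**

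| Route | F25 item 1 | F4 | Section E |
|---|---|---|---|
| PaO2/FiO2 <300 | yes | yes | yes |
| SpO2 <90%, room air | yes | yes | yes |
| SpO2 <90%, on oxygen | not listed | yes | yes |
| SpO2/FiO2 <315 | yes | yes | yes |
| Other clinical evidence | yes | no | no |

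The screen is narrower on the last row only, and wider on the third.

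**2. How wide the measured items are.** The ratio item is YES when SpO2 < 315 × FiO2. With Section E's FiO2 values:
- 3 L: 315 × 0.27 = 85.05, so the <90% item already decides.
- 4 L: 315 × 0.30 = 94.5.
- 5 L: 315 × 0.35 = 110.25, so any recorded SpO2 is YES (100/0.35 = 286).

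F25 uses other FiO2 values at some flows, but this does not narrow the screen. At 3 L F25's threshold is 315 × 0.25 = 78.75, below Section E's. At 6–7 L both thresholds exceed 100 (141.75 and 126). A recipient with four recorded NO answers and cyanosis should therefore be rare.

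**3. Answer patterns.** Four items with three answers give 3^4 = 81 patterns.
- No YES: 2^4 = 16 patterns.
- All NO: 1 pattern, which stops.
- At least one NR and no YES: 16 − 1 = 15 patterns, with no stated action.

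These are patterns, not frequencies; the protocol gives no frequency of NR. Without a blood gas the PaO2/FiO2 item has no value, so normal oximetry alone can lead to an unassigned pattern unless the coordinator enters NO for a test not done.

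**4. The plan's own figures.**
- Review numbers (Table-4): 2,590 × 0.40 = 1,036; × 0.50 = 518; × 0.60 = 310.8, or 311. Stopped: 518 − 311 = 207.
- Pilot (F6): 3 + 12 = 15 recipients with edema and 2 + 6 = 8 with hypoxemia, so 7 would stop. The pilot used the two ratios only, taken from laboratory records, and did not test a clinical limb.
- Power (Appendix D): 1,175 per arm, 2.32% vs 0.79%, one-sided 0.05, exact conditional test. Recomputed power is 0.9002, so the stated 90% reproduces.

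**5. What the planning rates contain.** Appendix D builds both rates from 7 TRALI cases in 6,888 components in the cited retrospective review. B3 says that review screened first on arterial blood gases (PaO2/FiO2 of 300 or less) and looked at radiographs only after that. Cases recognizable only by cyanosis, or without a blood gas, were therefore not counted in the 7.

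**6. Direction across arms.** If a fraction s of true cases is retained in both arms, the observed ratio is (s × p1)/(s × p0) = p1/p0. Incidence is understated by the factor s; the ratio is unchanged.

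**The case against.** The strongest reply is that the practical loss is small and partly handled already.

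- **The certain loss is nearly empty.** It needs four recorded NO answers together with clinical evidence. This stands: step 2 shows how wide the measured items are.
- **NR does not trigger a stop.** A reader might infer that recipients with unrecorded oxygenation are stopped and labeled as not having TRALI. The form stops only on all NO, and F25 item 6 gives that label only when bilateral infiltrates are absent. This stands. What remains is an undefined action, with F4 and G1 leaning towards stopping.
- **Power.** A reader might scale 2.32% and 0.79% down by 10% and report power falling from 90.0% to 86.7%. That would subtract cases the planning rates never contained (step 5), so the reduction does not follow.
- **The 207 charts.** They are recipients planned to have no hypoxemia, from a deliberately conservative workload assumption. They do not count missed cases, and neither do the pilot's 7 of 15.
- **Appendix H.** The blinded re-estimation of incidence after 33% of subjects would reflect a low yield and could raise the sample size. That protects power, but it neither recovers missed cases nor corrects the incidence estimates.
- **Other documents.** The Manual of Procedures, the SOP and coordinator training may define NR. They could settle that part. They would not supply the missing limb without changing F4 and the form.
- **G1 discloses limits.** It says that milder cases and unrecorded findings may be missed, and claims comprehensive detection only for clinically significant TRALI. It does not disclose that the screen omits part of F25.

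**Conclusion.** The inconsistency is in the text and worth correcting. F4 and Section E omit F25's clinical-evidence limb, and Section E leaves 15 answer patterns without an action.

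The number of cases affected cannot be derived from the protocol. The expected effect is some under-ascertainment in both arms and possibly different handling between sites. A bias between arms might be suspected from charting differences across hospitals, but the documents do not support it: the reviewers, triage physician and Board are blinded to antibody status, and control donors are frequency-matched by gender and parity within each center.

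The conclusion rests on two assumptions: that NR means no value was recorded, as Note 15 uses it elsewhere on the form, and that no unseen procedure lets a stopped chart reach the panel.

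**What to change.** 1. Reconcile F4, F25 and Section E so that the screen is at least as wide as F25. The simplest way is to add F25's existing clinical-evidence wording, with the six-hour window, as a fifth item in Section E and in F4. This adds no new criterion. Whether F25 itself should keep that limb is for the sponsor to decide.
2. State the action for NR. A chart with every oxygenation item NR should go forward to detailed review and not count as normal. For mixed NO and NR, one workable rule is to stop only if at least one measurement was recorded, none met a threshold, and there is no clinical evidence.

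**Cost.** One form line, one rule and some extra chart reviews. Section N implies 3 h + 1 h + 0.25 h = 4.25 h per chart for review, slides and transmission.
- If 10% of the 207 stopped charts go forward (an assumption, about 21 charts): 21 × 4.25 = about 89 h over five centers, or about 18 h each.
- Upper bound, all 207: 207 × 4.25 = about 880 h, or about 176 h per center.

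Both are below the 40% contingency of 413 h per center, although that margin must also cover access delays and any sample-size increase. The triage physician and the Board would see correspondingly more charts.
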